### Appendix 3. Management of Clinical and Laboratory Adverse Events

**Appendix 4. Mayo Scoring System for Assessment of Ulcerative Colitis Activity**

Stool Frequency – Each subject serves as his or her own control to establish the degree of abnormality of the stool frequency
	
 0 Normal number of stools for subject
 
 1 1 to 2 stools per day more than normal
 
 2 3 to 4 stools more than normal
 
 3 <math>\geq 5</math> stools more than normal

Rectal Bleeding – The daily bleeding score represents the most severe bleeding of the day.
	
 0 No blood seen
 
 1 Streaks of blood with stool less than half the time
 
 2 Obvious blood with stool half or more than half of the time
 
 3 Blood alone passes

Endoscopic findings – Assessed by Central Reader (include only for MCS assessment)
	
 0 Normal or inactive disease
 
 1 Mild Disease (erythema, decreased vascular pattern)
 
 2 Moderate Disease (marked erythema, lack of vascular pattern, friability, erosions)
 
 3 Severe Disease (spontaneous bleeding, ulceration)

Physician's Global Assessment – The physician's global assessment acknowledges the three other criteria, the subject's daily recollection of abdominal discomfort and general sense of well-being, and other observation, such as physical findings and the subject's performance status.
	
 0 Normal
 
 1 Mild disease
 
 2 Moderate disease
 
 3 Severe disease

**Appendix 5. CTCAE Grading Scale for Severity of Adverse Events**

Please refer to the Common Terminology Criteria for Adverse Events (CTCAE) Version 4.03, which can be found at:

[http://evs.nci.nih.gov/ftp1/CTCAE/CTCAE\\_4.03\\_2010-06-14\\_QuickReference\\_8.5x11.pdf](http://evs.nci.nih.gov/ftp1/CTCAE/CTCAE_4.03_2010-06-14_QuickReference_8.5x11.pdf)

For AEs associated with laboratory abnormalities, the event should be graded on the basis of the clinical severity in the context of the underlying conditions; this may or may not be in agreement with the grading of the laboratory abnormality.

The only modification to the CTCAE criteria is the addition of a Grade 1 upper respiratory infection as follows:

CTCAE v4.0 Term	Grade 1	Grade 2	Grade 3	Grade 4	Grade 5	CTCAE v4.03 AE Term Definition
Upper respiratory infection	Mild symptoms; symptomatic relief (eg, cough suppressant, decongestant)	Moderate symptoms; oral intervention indicated (eg, antibiotic, antifungal, antiviral)	IV antibiotic, antifungal, or antiviral intervention indicated; radiologic, endoscopic, or operative intervention indicated	Life-threatening consequences; urgent intervention indicated	Death	A disorder characterized by an infectious process involving the upper respiratory tract (nose, paranasal sinuses, pharynx, larynx, or trachea).

## **Appendix 6. Pregnancy Precautions, Definition for Female of Childbearing Potential, and Contraceptive Requirements**

The administration of filgotinib in embryo-fetal animal development studies resulted in decreased numbers of viable rat fetuses, increased resorptions, and visceral and skeletal malformations. Similar effects were noted in the rabbit. A safety margin relative to human exposure has not been identified. Pregnancy is contraindicated during use of filgotinib.

For participation in this study, the use of *highly effective* contraception is required as outlined below for all subjects who are of childbearing potential. In addition, during the study women of childbearing potential must have at a minimum, a urine pregnancy test every 4 weeks.

### **1) Definitions**

#### **a) Definition of Childbearing Potential**

For the purposes of this study, a female-born subject is considered of childbearing potential following the initiation of puberty (Tanner stage 2) until becoming post-menopausal, unless permanently sterile or with medically documented ovarian failure. Women who do not meet below criteria for being post-menopausal, are not permanently sterile, or do not have medically documented ovarian failure must have pregnancy testing as outlined by the protocol.

Women are considered to be in a postmenopausal state when they are  $\geq 54$  years of age with cessation of previously occurring menses for  $\geq 12$  months without an alternative cause.

Permanent sterilization includes hysterectomy, bilateral oophorectomy, or bilateral salpingectomy in a female subject of any age. Bilateral tubal ligation is not considered permanent sterilization.

#### **b) Definition of Male Fertility**

For the purposes of this study, a male-born subject is considered fertile after the initiation of puberty unless permanently sterilized by bilateral orchidectomy or has medical documentation of permanent male infertility. Vasectomy is not considered permanent sterilization.

### **2) Contraception for Female Subjects**

#### **a) Study Drug Effects on Pregnancy and Hormonal Contraception**

Filgotinib is contraindicated in pregnancy as there is a possibility of human teratogenicity/fetotoxicity in early pregnancy based on non-clinical data. Data from a drug-drug interaction study of filgotinib and hormonal contraceptives (GS-US-417-3916) have demonstrated co-administration with filgotinib did not alter the pharmacokinetics of representative hormonal contraceptives, levonorgestrel/ethinyl estradiol.

For female subjects, hormonal contraceptives will be permitted as a form of contraception when used in conjunction with a barrier method (preferably a male condom). For male subjects, male condom should be used; for their female partners of childbearing potential, an accepted contraceptive method should also be considered. Details are outlined below.

Please refer to the latest version of the filgotinib IB for additional information.

#### **b) Contraception for Female Subjects of Childbearing Potential**

The inclusion of female subjects of childbearing potential requires the use of highly effective contraceptive measures. Women must have a negative serum pregnancy test at screening and a negative urine pregnancy test on the Day 1 visit prior to randomization. Pregnancy tests will be performed at monthly intervals thereafter. In the event of a delayed menstrual period (> one month between menstruations), a pregnancy test must be performed to rule out pregnancy. This is true even for women of childbearing potential with infrequent or irregular periods.

Female subjects must agree to use one of the following methods from screening until 35 days following the last dose of study drug.

- Complete abstinence from intercourse of reproductive potential. Abstinence is an acceptable method of contraception only when it is in line with the subject's preferred and usual lifestyle.

Or

- Consistent and correct use of 1 of the following methods of birth control listed below.
  - Intrauterine device (IUD) with a failure rate of < 1% per year
  - Tubal sterilization
  - Essure micro-insert system (provided confirmation of success 3 months after procedure)
  - Vasectomy in the male partner (provided that the partner is the sole sexual partner and had confirmation of surgical success 3 months after procedure)

Female subjects who wish to use a hormonally based method, must use it in conjunction with a barrier method; the barrier method is to be used either by the female subject or by her male partner. Female subjects who utilize a hormonal contraceptive as one of their birth control methods must have consistently used the same method for at least three months prior to study dosing. Hormonally-based contraceptives and barrier methods permitted for use in this protocol are as follows:

- Hormonal methods (each method *must* be used with a barrier method, preferably male condom)
  - Oral contraceptives (either combined estrogen/progestin or progesterone only)
  - Injectable progesterone
  - Implants of levonorgestrel

- Transdermal contraceptive patch
- Contraceptive vaginal ring
- Barrier methods (each method *must* be used with a hormonal method)
  - Male or female condom with or without spermicide
  - Diaphragm with spermicide
  - Cervical cap with spermicide
  - Sponge with spermicide

All female subjects must also refrain from egg donation and in vitro fertilization during treatment and until at least 35 days after the last study drug dose.

### 3) Contraception Requirements for Male Subjects

It is theoretically possible that a relevant concentration of study drug may be achieved in a female partner from exposure to the male subject's seminal fluid. Therefore, male subjects with female partners of childbearing potential must use condoms during study participation and for 90 days after the last study drug dose. Female partners of male study subjects should consider using one of the above methods of contraception as well. Male subjects must also refrain from sperm donation during treatment and until at least 90 days after the end of study drug dosing.

### 4) Unacceptable Birth Control Methods

Birth control methods that are unacceptable include periodic abstinence (eg, calendar, ovulation, symptothermal, post-ovulation methods), withdrawal (coitus interruptus), spermicides only, and lactational amenorrhea method (LAM). Female condom and male condom should not be used together.

### 5) Procedures to be Followed in the Event of Pregnancy

Subjects will be instructed to notify the investigator if they become pregnant at any time during the study, or if they become pregnant within 30 days of last study drug dose. Subjects who become pregnant or who suspect that they are pregnant during the study must report the information to the investigator and discontinue study drug immediately. Subjects whose partner has become pregnant or suspects she is pregnant during the study are to report the information to the investigator.

Instructions for reporting pregnancy, partner pregnancy, and pregnancy outcome are outlined in Section 7.7.2.1.

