#### **5.4. Prior and Concomitant Medications**

All medications taken up to 30 days prior to the screening visit through the end of study (30 days after the last dose of study drug), need to be recorded in the source documents and on the eCRF. At each study visit, the study center will record any and all medications taken by the subject since the last visit or during the visit (as applicable). All concomitant medications (prescription, peri-procedural medications, over-the-counter medications, including vaccines, vitamins, herbal, dietary supplements, and minerals) must be recorded in the concomitant therapy section of the eCRF.

Effective current therapies should not be discontinued for the sole purpose of participating in this study. Subjects may receive medications as supportive care or to treat AEs as deemed necessary by the Investigator or the subject's physician. Should subjects have a need to initiate treatment with any excluded concomitant medication, the Gilead Medical Monitor should be consulted prior to initiation of the new medication. In instances where an excluded medication is initiated prior to discussion with the Sponsor, the Investigator should notify Gilead as soon as he/she is aware of the use of the excluded medication.

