#### 6.5. Post-Treatment Assessments

All subjects must complete the PTx assessments 30 days after the last dose of study drug. Subjects who enter into the LTE study (GS-US-418-3899) will not complete PTx assessments associated with this protocol.

The following will be performed and documented:

- Symptom directed PE
- Obtain body weight and vital signs (resting blood pressure, respiratory rate, pulse and temperature)
- Review AEs and concomitant medications

- Obtain blood samples (reference Study Procedure Table in [Appendix 2](#))
- Obtain urine sample (reference Study Procedures Table [[Appendix 2](#)])
  - Pregnancy test (for females of child bearing potential only)

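### Appendix 6 asks subjects to report pregnancies only to about 30 days after last dose, although it requires contraception to day 35 in women and condom use to day 90 in men

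*Protocol*

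**What the plan says.** **Notification by subjects (Appendix 6, item 5).** A female subject is to tell the investigator of a pregnancy during the study, "or if they become pregnant within 30 days of last study drug dose". For men the sentence is: "Subjects whose partner has become pregnant or suspects she is pregnant during the study are to report the information to the investigator". It gives no number of days after last dose.

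**Contraception (Appendix 6, items 2b and 3).** For women: "Female subjects must agree to use one of the following methods from screening until 35 days following the last dose of study drug". Men with partners of childbearing potential "must use condoms during study participation and for 90 days after the last study drug dose". The limits on egg donation (35 days) and sperm donation (90 days) use the same periods, both in Appendix 6 and in the exclusion criteria in Sections 4.2.2 and 4.5.2.

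**End of follow-up for a subject.** Section 5.4 records medications "through the end of study (30 days after the last dose of study drug"). Section 6.5 says: "All subjects must complete the PTx assessments 30 days after the last dose of study drug". Subjects who enter the LTE study "will not complete PTx assessments associated with this protocol". Section 3.7 defines a trial-wide end of study: the last subject's 58 weeks of treatment plus 30 days.

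**Reporting by investigators (Section 7.7.2.1).** Pregnancies in female subjects are reportable if identified up to the end of post-drug follow-up. Partner pregnancies are reportable with no stated end date. Serious adverse pregnancy outcomes after the study are also reportable.

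**The concern.** The protocol sets its own periods for reproductive precautions, 35 and 90 days, and uses them consistently except in the instruction that would tell the sponsor when the precaution has failed. That instruction stops at the general 30-day safety follow-up.

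Filgotinib is contraindicated in pregnancy. The introduction to Appendix 6 says that no safety margin against human exposure has been established, and Section 1.4 names contraception as the mitigation for the malformations seen in rats and rabbits. A conception while contraception is still compulsory is a failure of that mitigation, and the sponsor would want to follow its outcome. A subject and a site that follow the text exactly could leave such a pregnancy unreported. What is at stake is the completeness of pregnancy reporting. No endpoint, sample size, error rate or analysis is touched.

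**Working it through.** No statistical figure has to be reproduced. The check compares the stated periods, all counted from the subject's last dose.

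| | Contraception required to | Subject told to notify to | Days not covered |
|---|---|---|---|
| Female subject | day 35 (Appendix 6, item 2b) | day 30 (Appendix 6, item 5) | 35 − 30 = 5 (days 31-35) |
| Partner of male subject | day 90 (Appendix 6, item 3) | end of the study, taken as day 30 (Sections 5.4 and 6.5) | 90 − 30 = 60 (days 31-90) |

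**Visit window.** If a man's participation ends at the post-treatment visit itself, which has a window of ±3 days, the partner gap is 90 − 33 = 57 to 90 − 27 = 63 days.

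**Alternative reading.** Suppose *during the study* means the trial-wide end in Section 3.7. Let D be the subject's last dose and L the last subject's last dose, so that the study ends at L + 30.

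- Partners: the gap is zero when D + 90 ≤ L + 30, that is D ≤ L − 60. Otherwise it is 60 − (L − D) days.
- Women: the gap is zero when D + 35 ≤ L + 30, that is D ≤ L − 5. Otherwise it is 5 − (L − D) days.

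**Which reading fits the text.** L is never earlier than D, so L + 30 is never earlier than D + 30. Under the trial-wide reading, the separate 30-day clause for female subjects would therefore add nothing for anyone. A limit counted from the subject's own last dose makes sense only if *during the study* does not already run past it. Appendix 6 item 3 also treats study participation and the 90 days after last dose as separate periods. The per-subject reading is the natural one.

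**Does Section 7.7.2.1 close the gap?**

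- *Female subjects.* The duty covers pregnancies identified up to the end of follow-up, which is the 30-day visit. A pregnancy test on day 30 cannot show a conception on days 31-35. Such a pregnancy becomes reportable only if it has an adverse outcome.
- *Partners.* The investigator's duty has no time limit, so 0 days are missing from it. But it operates only if the site hears of the pregnancy. The route that Appendix 6 sets out is the man's own report, and that is limited to the study. No later contact is scheduled.

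**Who is affected.** Women of childbearing potential, and men with partners of childbearing potential, who do not enter the LTE: for example those who opt out, or who worsen, need prohibited medication and so do not qualify (Section 3.6). The documents do not give their number.

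**The case against.** The case against has five parts.

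- **The partner gap is inferred.** The 30-day phrase covers only subjects who themselves become pregnant, and the section that defines the end of study is trial-wide. This stands as far as the partner figure depends on a reading, with 0 as its lower bound. The wording of item 5 and the separation made in item 3 still favour the per-subject reading.
- **Harm is largely covered elsewhere.** Partner pregnancies are reportable without limit, and Section 7.3.2 has investigators report any relevant serious event they learn of after participation ends. A congenital anomaly counts as serious, and so does a spontaneous abortion. This stands, and it keeps the point small. Each route nevertheless depends on the site being told, and the instruction to subjects is what makes that likely. It is fair to add that a wording change without a new contact also relies on subjects to report.
- **The periods need not match.** Thirty days is the general adverse-event follow-up, and a contraception period may carry a margin. This explains the 30 days, but a conception inside the compulsory period still breaches a stated precaution. The periods are precautionary and not proven exposure windows. For transfer through semen the protocol says only: "It is theoretically possible that a relevant concentration of study drug may be achieved in a female partner".
- **The consent form may say more.** It is not available here. If it already asks for reports to 35 and 90 days, the practical gap disappears and only the inconsistency remains.
- **Numbers are unknown.** This is correct. The day counts are calendar days in an instruction, not shares of pregnancies missed.

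**Conclusion.** The point holds as a minor inconsistency in safety reporting. For women the 5-day shortfall is explicit in the text. For partners it is 60 days if a man's study ends 30 days after his last dose, and between 0 and 60 days if the trial-wide end of study is meant. The investigator's open-ended duty on partner pregnancies and the reporting of adverse outcomes reduce the consequence but do not remove the gap in what subjects are told. The conclusion is limited to subjects who do not enter the LTE, and its practical weight assumes that the consent form does not give a longer instruction. Few such conceptions are to be expected, though the documents offer no figure.

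**What to change.** 1. In Appendix 6, item 5, ask subjects to notify any pregnancy of their own conceived up to 35 days after last dose, and any partner pregnancy conceived up to 90 days after last dose.
2. In Section 7.7.2.1, have investigators report pregnancies in female subjects conceived within 35 days of last dose, even when they are identified after the post-treatment visit.
3. Remind subjects of both periods at their last visit, unless the consent form already does so.

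Contraception periods, visits and pregnancy tests stay as they are. The cost is wording in two protocol sections and a short reminder. The downside is a few more pregnancy reports and some follow-up after the post-treatment visit.

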### 6) Pregnancy Testing

All females of childbearing potential will have urine pregnancy testing every 4 weeks (in clinic) during their study participation. If a urine pregnancy test is positive, the subject should stop study drug immediately, contact the investigator, and have confirmatory serum pregnancy test in clinic.

EQ-5D	EuroQoL (health-related quality of life questionnaire)
ET	early termination
FAS	Full Analysis Set
FDA	Food and Drug Administration
Gilead	Gilead Sciences, Inc.
HCRU	health care resource utilization
HLGT	high-level group term
HLT	high-level term
HRQoL	health-related quality of life
hs-CRP	high-sensitivity C-reactive protein
IBD	inflammatory bowel disease
IBDQ	Inflammatory bowel disease questionnaire
ID	identification
IVRS	interactive voice response system
IWRS	interactive web response system
LLOQ	lower limit of quantitation
LLT	lower-level term
LOCF	last observation carried forward
LOQ	limit of quantitation
LTE	long-term extension
MCS	Mayo Clinic Score composed of subscores from endoscopy, rectal bleeding, stool frequency, and physician's global assessment

M-Day	maintenance study day
MedDRA	Medical Dictionary for Regulatory Activities
MST	MedDRA search term
MMP-9	matrix metalloproteinase-9
OL	open label
Partial MCS	all components of MCS except for endoscopic subscore
PD	pharmacodynamics
PGA	Physician's Global Assessment
PK	pharmacokinetic
PP	Per Protocol
PT	preferred term
PTM	placebo-to-match
Q1, Q3	first quartile, third quartile
SAE	serious adverse event
SAP	statistical analysis plan
SD	standard deviation
SE	standard error
SF-36	short-form 36 health survey
SMQ	Standardised MedDRA Queries
SOC	system organ class
SOP	standard operation procedure
TEAE	treatment-emergent adverse event
TFLs	tables, figures, and listings
TNF α	tumor necrosis factor-alpha
UC	ulcerative colitis
UCEIS	ulcerative colitis endoscopic index of severity
ULN	upper limit of normal
US	United States
V-Day	visit day
WHO	World Health Organization
WPAI	Work Productivity and Activity Impairment

PHARMACOKINETIC ABBREVIATIONS

AUC_{last}	the area under the concentration versus time curve from time zero to the last quantifiable concentration
AUC_{tau}	area under the concentration versus time curve over the dosing interval
C_{max}	the maximum observed serum/plasma/peripheral blood mononuclear (PBMC) concentration of drug
C_{tau}	observed drug concentration at the end of the dosing interval
CL_{ss}/F	apparent oral clearance after administration of the drug: at steady state: $CL_{ss}/F = Dose/AUC_{tau}$, where "Dose" is the dose of the drug
T_{max}	the time (observed time point) of C_{max}

1. INTRODUCTION

This statistical analysis plan (SAP) describes the statistical analysis methods and data presentations to be used in tables, figures, and listings (TFLs) in the clinical study report (CSR) for Study Protocol GS-US-418-3898. This SAP is based on the study protocol amendment 5 dated 02 April 2019 and the electronic case report form (eCRF). The SAP will be approved before database finalization of the final analysis. Any changes made after the finalization of the SAP will be documented in the CSR.

1.1. Study Objectives

The overall objective of the study is to evaluate the effect of treatment with filgotinib on the induction and maintenance of remission in subjects with moderately to severely active ulcerative colitis (UC). Subject who are biologic-naïve and biologic experienced will be enrolled in Cohort A and Cohort B respectively. Treatment assignments will be randomized within each cohort.

1.1.1. Primary Objectives

The primary objectives are:

Induction Studies (Cohort A Induction Study and Cohort B Induction Study)

- To evaluate the efficacy of filgotinib as compared to placebo in establishing endoscopy/bleeding/stool (EBS) remission at Week 10

Maintenance Study

- To evaluate the efficacy of filgotinib as compared to placebo in establishing EBS remission at Week 58

